9. The anti-tTG and anti-DGP antibody tests at the screening visit will include both IgA and IgG. At all other visits, only anti-tTG IgA and anti-DGP IgA will be tested.
10. Blood samples for biomarker analyses should be taken prior to study drug administration. The time and date of these samples must be accurately recorded.
11. The study drug administered at Visits 1 and 2 (single-blind run-in period) is placebo for all subjects.
12. The baseline EGD and biopsy can be performed within 12 days before Visit 2.
13. The final EGD and biopsy can be collected within 7 days before Visit 15. A final or early termination EGD and biopsy are required for all subjects. Subjects with early termination should undergo the EGD and biopsy unless a medical condition precludes it, at the Investigator's discretion.
14. Subjects are required to answer the stool frequency question (stools of Type 6 or 7 on BSFS) daily before bedtime in the eDiary.
15. The CeD PRO is captured daily in the eDiary after the last meal of the day before the subject goes to bed.
16. Subjects are instructed to record PGIC and PGIS every other week in the eDiary.
17. Treatment-emergent adverse events are collected from the first dose of the post-randomization study drug administration (Visit 3) through the final visit. Between signing the informed consent form and the first dose of study drug (including the single-blind run-in period), only AEs related to study procedures and SAEs will be recorded.

2. Introduction

PRV-015, also known as AMG 714, is a monoclonal antibody (mAb) targeting interleukin (IL) 15 (IL-15). It is being developed as an adjunct to a gluten-free diet (GFD) for the treatment of non-responsive celiac disease (NRCD).

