At the end of the 4-week single-blind, placebo run-in period, subjects will return to the study site for Visit 3 (Week 0/Day 1) and be re-evaluated for inclusion/exclusion criteria. Those who meet the entry criteria at this time will enter the 24-week double-blind treatment period (from Visit 3 to Visit 15). At the same visit, eligible subjects will be randomized in a 1:1:1:1 ratio to receive 100 mg, 300 mg, or 600 mg PRV-015, or matching placebo, subcutaneously (SC) every 2 weeks (q2w). Randomization will be stratified by VH:CD of <2 or ≥ 2 and by the CeD PRO Abdominal Symptoms domain score of <3 or ≥ 3 at baseline using the average of the Abdominal Symptoms domain scores over the last week of the placebo run-in period immediately before randomization. Enrollment of subjects with Marsh score of 0 or 1 will be capped at approximately 72 subjects, although fewer than 72 may be enrolled.

The study drug (1 of the 3 doses of PRV-015 or placebo) will be administered SC q2w in the double-blind treatment period through Visit 14. Each dose will be administered in a double-blind fashion. The subjects' adherence to GFD will be assessed retrospectively throughout the study using the stool and urine gluten tests based on the G12 antibody to interpret possible dietary changes or transgressions. Results will not be communicated to the subjects, who will be instructed to continue their baseline dietary habits throughout the study.

Subjects will be assessed for efficacy and safety throughout the study, as indicated in the Schedule of Activities (SoA) (Section 1.3). Clinical assessments occur from Visit 3 through Visit

16. Safety is also assessed at each on-site visit through the end-of-study visit (Visit 16), which takes place 6 weeks after the last planned dose of the study drug.

Randomized subjects will undergo a second EGD and biopsy at the end of the 24-week treatment period, within 7 days of Visit 15 in order to assess changes from baseline in IELs and VH:CD.

Visits 6, 8, 10, and 12 may be conducted either at the site or remotely by certified mobile personnel per the Investigator's decision.

All subjects enrolled in the study will complete the daily eDiary for CeD PRO (at the end of the subject's daily activities, when no more food will be consumed) and for the stool frequency question from Visit 1 through the end of the study at Visit 16, which will encompass the single-blind placebo run-in and the double-blind treatment period and a safety follow-up period.

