8.6. Pharmacokinetics and Immunogenicity

Blood samples will be collected at Visit 3 before the first post-randomization dose of study drug administration (baseline) and before the dose is given at each subsequent visit indicated in the SoA. Samples will be analyzed for serum trough concentration of PRV-015 (C_{min}) and ADA, as well as neutralizing antibodies (NAb), using validated assays.

Drug concentration information will not be reported to investigative sites or blinded personnel until the study is unblinded.

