9.4.6. Pharmacokinetic and PK/PD Analyses

The geometric means and geometric CV% of PRV-015 minimum concentrations (C_{min}) will be reported by treatment group and time point in addition to N, mean, SD, min, and max. In

addition, dose proportionality, achievement of steady-state, and accumulation ratio based on C_{min} will be assessed. Associations of C_{min} with biomarkers of disease activity and other clinical endpoints may be explored. Dose proportionality will be analyzed using a power model, and potential PK/PD associations will mainly be assessed graphically and, if warranted, further elucidated with linear or nonlinear modeling techniques.

Additionally, absolute and changes from baseline in gluten-induced serum antibodies (anti-tTG and anti-DGP antibodies) will be listed and summarized by treatment group and collection visit. Relationships to dose and PK may be explored.

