8.2.3 Imputing Missing Values

Primary Endpoint

Imputation of missing values for sensitivity analysis of the primary endpoint is described in detail in Section 8.6.1.3.

BSFS Stools of Type 6 or 7

Weekly scores are calculated by summing the previous 7 days. Missing days within a given week will be imputed as the average of the non-missing days for a given assessment week for the derivation

of weekly sums. Weekly score is calculated if there are at least 4 non-missing daily scores available. If there are less than 4 non-missing daily scores, weekly score will be counted as missing.

Laboratory Assessments

For all clinical laboratory assessments, values below the lower limit of quantitation (LLQ) will be assigned a value of 0.5 x LLQ for summary statistics and values over the upper limit of quantitation (ULQ) will be assigned a value of ULQ for summary statistics.

PK Concentrations

PRV-015 concentrations below the LLQ will be assigned a value of 0.5 x LLQ in mean calculations for the summary of PRV-015 concentrations.

Missing and Partial Dates

Missing dates for Adverse Events and Concomitant Medications

For completely missing AE or CM start dates, the following applies:

- If end date is missing or it is after the start of the DB treatment date, then the start of the DB treatment date is used.
- If end date is in the SB placebo run-in phase, the start date of the event is imputed as the start of the SB placebo run-in date.
- If end date is in the screening phase, the start date of the event is imputed as the start of the screening date.

For completely missing end dates, the event is considered to be ongoing. No imputation will be done on completely missing end dates.

Partial dates for Adverse Events and Concomitant Medications

For partial start and end dates, the minimum possible date is imputed for start date and maximum possible date is imputed for end date. For example, if partial start date is "SEP2020" and partial end date is "OCT2020" then the imputed start date is "01SEP2020" and the imputed end date is "31OCT2020".

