8.8.1.1 Serum Concentration Data

All PK concentrations will be reported and analyzed with the same precision as the source data provided by the bio-analytical laboratory regardless of how many significant figures or decimals the data carry.

A listing of PK blood sample collection times will be provided. Serum concentrations will be summarized using descriptive statistics by time point for PRV-015 treatment groups. Concentrations that are below the limit of quantitation (BLQ) will be treated as zero for the computation of descriptive statistics. Descriptive statistics for concentration time data will include n, mean, standard deviation (SD), median, Lower Quartile, Upper Quartile, minimum, maximum, Geometric mean and Geometric Coefficient of Variation (GCV). For the reporting of descriptive statistics, the mean, standard deviation and Geometric mean will be presented to one digit more precision than the source data. The minimum, median, maximum, Lower Quartile and Upper Quartile will be presented to the same precision as the source data. Geometric Coefficient of Variation will always be reported to 1 decimal place. A minimum of n=3 is required for all descriptive statistics to be generated. If n is less than 3, only N, n, minimum, and maximum will be reported.

A subject listing of all concentration time data for each treatment will be presented. Figure of arithmetic mean concentration-time data (\pm SD, as appropriate) will be presented for PRV-015 treatment on linear and semi-logarithmic scales. Individual subject concentration-time data will be graphically presented on linear and semi-logarithmic scales.

No imputations will be done for missing data. Individual concentrations will be reported to the same precision as the source data.

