8.8.1.2 Pharmacokinetic Analysis

Pharmacokinetic analysis will be done on PK analysis set.

PRV-015 trough concentrations (C_{min}) is the trough concentration which will be the pre-dose concentration for respective visits. PRV-015 trough concentrations (C_{min}) will be summarized using descriptive statistics by time point for PRV-015 treatment groups. Concentrations that are below the limit of quantitation (BLQ) will be treated as zero for the computation of descriptive statistics. Descriptive statistics for concentration time data will include n, mean, standard deviation (SD), median, Lower Quartile, Upper Quartile, minimum, maximum, Geometric mean and Geometric Coefficient of Variation (GCV). For the reporting of descriptive statistics, the mean, standard deviation and Geometric mean will be presented to one digit more precision than the source data. The minimum, median, maximum, Lower Quartile and Upper Quartile will be presented to the same precision as the source data. Geometric Coefficient of Variation will always be reported to 1 decimal place. A minimum of n=3 is required for all descriptive statistics to be generated. If n is less than 3, only N, n, minimum, and maximum will be reported.

In addition, dose proportionality, achievement of steady-state, and accumulation ratio based on Cmin will be assessed.

Dose Proportionality:

Dose proportionality of C_{min} will be assessed separately for PK sampling Day 15 (Visit 4) and Day 169 (Visit 15) using the power model (C_{min} = a * Dose^{β}), along with an "estimation" interpretation, according to the recommendations in Gough et al. (1995). The power model will be fitted on the log-transformed scale as:

 $log(Y_i)=a + \beta*log(Dose_i)+\epsilon_i$

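### The SAP gives two conflicting values (0.5 x LLQ and zero) for PRV-015 concentrations below quantitation, and the zero rule cannot yield the geometric CV that the plan requires

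*SAP*

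**What the plan says.** SAP 8.2.3, under PK Concentrations, reads: "PRV-015 concentrations below the LLQ will be assigned a value of 0.5 x LLQ in mean calculations for the summary of PRV-015 concentrations".

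SAP 8.8.1.1 (serum concentrations) and SAP 8.8.1.2 (Cmin) each carry the other rule: "Concentrations that are below the limit of quantitation (BLQ) will be treated as zero for the computation of descriptive statistics". In both sections the statistics that follow are n, mean, SD, median, quartiles, minimum, maximum, geometric mean and geometric CV. The only relief from the full list is for cells with n below 3.

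Protocol 9.4.6 independently commits to "The geometric means and geometric CV% of PRV-015 minimum concentrations", by treatment group and time point. SAP 3.2 names Cmin as the secondary PK endpoint.

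SAP 8.8.1.1 also asks for mean and individual concentration-time figures that "will be presented for PRV-015 treatment on linear and semi-logarithmic scales". SAP 8.10, which lists departures from the protocol, does not mention values below quantitation.

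**The concern.** The same measured result takes two values depending on which section a programmer follows. Two people could both apply the SAP faithfully and produce different tables for the secondary PK endpoint.

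One of the two rules also does not work for statistics that the plan requires. Geometric statistics are built on logarithms, and a zero has none. Software may then return a missing value, return zero, or silently drop the subject and compute the geometric mean from the quantifiable values only. The plan does not say which is intended. If the choice is left until concentrations are being tabulated, it may be made with the data in view.

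**Working it through.** The plan states no figure to reproduce. The check is a comparison of texts plus a small illustration.

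**1. Can the two rules be reconciled?** One might read 8.2.3 narrowly: 0.5 x LLQ for means, zero for everything else. That fails, because the list governed by the zero rule itself names the mean and the geometric mean.

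**2. What does a zero do?** Geometric mean = exp(mean of ln x). Geometric CV = 100 x sqrt(exp(s²) − 1), where s² is the variance of ln x. With one zero, ln(0) is undefined, so s² and the geometric CV cannot be computed. The geometric mean is undefined on the log scale, or exactly 0 if computed as the root of a product.

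**3. Where would such values arise?**
- *Visit 3.* Protocol 8.6 places this sample before the first post-randomization dose, and the Schedule of Activities notes: "The study drug administered at Visits 1 and 2 (single-blind run-in period) is placebo for all subjects". Every value should be below quantitation. The mean is 0 under one rule and 0.5 x LLQ under the other. Under the second rule the geometric mean is also 0.5 x LLQ and the geometric CV 0%, which tells the reader nothing.
- *Visit 16.* Protocol 8.1 lists a trough sample at this visit, "which takes place 6 weeks after the last planned dose of the study drug": Day 197 − Day 155 = 42 days, or 3 dosing intervals of 14 days.
- *Subjects who stop study drug.* Protocol 7.1 encourages them to attend later on-site visits. The PK analysis set in SAP 8.1.6 keeps them if they have one evaluable postdose sample.

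**4. Illustration.** All inputs are assumed: 50 values in a cell, one below quantitation, the other 49 centred at m x LLQ. The LLQ is the unit.
- Arithmetic mean: 49m/50 with zero; (49m + 0.5)/50 with 0.5 x LLQ.
- Geometric mean with 0.5 x LLQ: exp((49 ln m + ln 0.5)/50).

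| m | Mean, zero | Mean, 0.5 x LLQ | Geo. mean, zero kept | Geo. mean, zero dropped | Geo. mean, 0.5 x LLQ |
|---|---|---|---|---|---|
| 5 | 4.90 | 4.91 | 0 or undefined | 5 | 4.775 (−4.5%) |
| 20 | 19.60 | 19.61 | 0 or undefined | 20 | 18.578 (−7.1%) |
| 100 | 98.00 | 98.01 | 0 or undefined | 100 | 89.945 (−10.1%) |

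Geometric CV at m = 20 with log-SD 0.5 among the 49:
- Without the low value: 100 x sqrt(exp(0.25) − 1) = 53.3%.
- With it at 0.5 x LLQ: s² = [48 x 0.25 + (49/50)(ln 40)²]/49 = (12 + 13.336)/49 = 0.517, giving 82.3%.
- With log-SD 0.3 the change is 30.7% to 65.9%; with 0.8 it is 94.7% to 120.7%.
- With the value at zero: not computable.

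**5. The models.** Both rules are worded for summaries. The power model, the accumulation ANOVA and the steady-state model in SAP 8.8.1.2 all work on the log scale, and no rule for values below quantitation is stated for them. The power model and the accumulation ratio use Days 15 and 169 only, so Visits 3 and 16 do not enter them. The steady-state model names no visits.

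**The case against.** The strongest reply is that the effect may be negligible. Visit 3 is the one place where values below quantitation are assured, and nobody needs a geometric mean there. Protocol 7.1 calls permanent discontinuation rare. SAP 8.8.1 allows minor changes to the design of tables and figures, and printing 'not calculated' or leaving a zero off a log axis plausibly falls under that. One might add that the PK section, being specific, overrides the general one.

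Much of this stands as to size, but it does not remove the conflict. Latitude over table design does not choose between two values for one result. The SAP states no precedence, and the section-specific rule is the one that fails. One might also argue that off-drug visits yield no Cmin, since SAP 8.8.1.2 defines Cmin as a pre-dose concentration. But Visit 15 has no dose either, and the same section uses it as the Day 169 Cmin.

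Several stronger readings are tempting and should be resisted:
- A reader might take "Geometric Coefficient of Variation will always be reported to 1 decimal place" as a promise of a geometric CV in every cell. It is a rounding rule, and the same paragraph drops the statistic when n is below 3. The requirement rests on the list of statistics and on Protocol 9.4.6.
- A reader might count the Visit 3 cells (10 PK visits x 3 dose groups = 30 cells, of which 3 are Visit 3) and call a tenth of the table defective. Those cells are uninformative under either rule.
- A reader might infer from the illustration that arithmetic means after dosing barely differ. That follows only for one low value in 50. Visit 16 could hold many more, and the documents do not say.

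**Conclusion.** The contradiction is in the text and needs no assumption. In any cell with n of at least 3 and at least one value below quantitation, the zero rule makes the geometric CV incomputable and the geometric mean zero or undefined. The SAP and Protocol 9.4.6 both require these statistics for Cmin.

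The documents give neither the LLQ nor the proportion of values below it, so how often this happens after dosing, and how much it matters, cannot be determined. The percentages above illustrate the mechanism under assumed inputs; they do not estimate impact. Nor do the documents support a claim that the PK models would be biased, only that their handling of such values is unstated.

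Severity is minor. The issue is confined to PK summaries and supportive PK modelling. Primary efficacy, power and safety analyses are unaffected.

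**What to change.** Make these changes before unblinding:

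- In SAP 8.8.1.1 and 8.8.1.2, replace the zero rule with the 0.5 x LLQ rule already in 8.2.3. Word all three places identically so that it covers every summary statistic. Show the number of values below quantitation in each cell.
- At the pre-first-dose visit, report no geometric mean or geometric CV and leave the visit off the semi-logarithmic plots. Record this in SAP 8.10 as a departure from Protocol 9.4.6.
- Add one sentence applying the same substitution to troughs below quantitation in the power, accumulation and steady-state models, and excluding the pre-first-dose sample from the steady-state model.

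Keeping zero and leaving geometric statistics blank wherever a low value occurs is a weaker alternative. It would extend the departure from Protocol 9.4.6 to every affected cell.

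The cost is a few edited paragraphs and no new data. The statistical price is that 0.5 x LLQ pulls the geometric mean down and inflates the geometric CV where low values occur. In the assumed case of one in 50, with the others at 20 x LLQ and log-SD 0.5, the geometric mean falls 7.1% and the geometric CV rises from 53% to 82%. The displayed counts let the reader see where this is happening.

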- HbA1C (subjects with diagnosed Type 1 or Type 2 diabetes only)
- Urinalysis (same tests as screening)
- Stool and urine gluten tests
- Urine pregnancy test (WOCBP only)
- Anti-tTG IgA, anti-DGP IgA
- Serum biomarkers (e.g., IL-15)
- Trough concentration of PRV-015
- ADA

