receive 100 mg, 300 mg, or 600 mg PRV-015, or matching placebo, subcutaneously (SC) every 2 weeks (q2w). Randomization will be stratified by baseline VH:CD of <2 or ≥2 and by the CeD PRO Abdominal Symptoms domain score of <3 or ≥3 at baseline using the average of the Abdominal Symptoms domain scores over the last week of the placebo run-in period immediately before randomization. A minimum of four daily recordings are required for derivation of the weekly mean Abdominal Symptoms domain score. Enrollment of subjects with Marsh score 0 or 1 will be capped at approximately 72 subjects, although fewer than 72 may be enrolled.

The study drug (1 of the 3 doses of PRV-015 or placebo) will be administered SC q2w in the double-blind treatment period through Visit 14. Each dose will be administered in a double-blind fashion. The subjects' adherence to GFD will be assessed retrospectively throughout the study using the stool and urine gluten tests based on the G12 antibody to interpret possible dietary changes or transgressions. Results will not be communicated to the subjects, who will be instructed to continue their baseline dietary habits throughout the study.

Subjects will be assessed for efficacy and safety throughout the study, as indicated in the Schedule of Activities (SoA) (Appendix 11.1). Clinical assessments occur from Visit 3 through Visit 16 of the double-blind randomized treatment period. Safety is also assessed at each on-site visit through the end-of-study visit (Visit 16), which takes place 6 weeks after the last planned dose of the study drug.

Randomized subjects will undergo a second EGD and biopsy at the end of the 24-week treatment period, within 7 days of Visit 15 in order to assess changes from baseline in IELs and VH:CD.

Visits 6, 8, 10, and 12 may be conducted either at the site or remotely by certified mobile personnel per the Investigator's decision.

[figure not shown]
All subjects enrolled in the study will complete the daily eDiary for CeD PRO (at the end of the subject's daily activities, when no more food will be consumed) and for the stool frequency question from Visit 1 through the end of the study at Visit 16, which will encompass the single-blind placebo run-in and the double-blind treatment period and a safety follow-up period.

Safety assessments include clinical laboratory tests, vital signs, and AE assessments. Subjects may undergo unscheduled visits if needed (e.g., for safety reasons).

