where Y_i and Dose; are the C_{min} value and dose value for subject i, respectively, ϵ_i is the random error, α is the intercept parameter and β is the slope parameter. The power model parameters will be estimated using least -squares (LS) regression and presented with 90% CIs. Model lack-of-fit will be assessed by residual plots, and by an F-test of the residual mean square versus the pure error residual mean square. If the model fit is adequate, point estimate and 90% CI for β will be obtained, and used to obtain point estimates and 90% CIs for the increase in C_{min} associated with an r-fold (r=2 and r=high dose / low dose) increase in dose, by exponentiating r to the power of the β point estimate and confidence limits, $r^{\beta \pm t \times SE(\beta)}$. If there is evidence of model lack-of-fit, then an ANOVA model on the log-transformed C_{min} with dose as fixed categorical effect will be used. Point estimate and 90% CI, associated with mean difference between pairwise dose increases, obtained from this model will be converted back to the original scale using the antilog transformation.

Accumulation ratio:

For C_{min} , individual accumulation ratio Rac C_{min} at Day 169 will be calculated as C_{min} at Day 169/ C_{min} at Day 15. A listings of individual accumulation ratios will be provided, along with their descriptive statistics (arithmetic mean, standard deviation, geometric mean, coefficient of variation (%), median, minimum and maximum).

Accumulation versus Day 15 (Visit 4) will be assessed for Day 169 (Visit 15) using an ANOVA model on the log-transformed accumulation ratio (Rac C_{min}) with dose as fixed categorical effect. Point estimates and 90% CI obtained, by dose level and overall, from this model will be converted back to the original scale using the antilog transformation.

Achievement of steady-state:

Steady state on Cmin (ie, Ctrough) will be assessed using a nonlinear mixed model (Hoffman et al, 2005):

$$C_{ij} = C_{ss}e^{c_i}(1 - e^{-(\gamma e^{g_i}j)})e^{\varepsilon_{ij}}$$

where C_{ij} is the observed trough (C_{min}) plasma concentration for the ith subject on Day j, C_{SS} is the average steady state trough (C_{min}) plasma concentration, γ is the average first-order elimination rate, $\epsilon_{ij} \sim N(0, \sigma^2_e)$ is the random within-subject error, and c_i and g_i are the random individual deviations from C_{SS} and γ , respectively, such that

 $(c_i, g_i) \sim N([0, 0], \Sigma)$ with

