$$\Sigma = \begin{bmatrix} \sigma_c^2 & \sigma_{cg} \\ \sigma_{cg} & \sigma_g^2 \end{bmatrix}$$

The model assumes a log-normal distribution for both the within-subject erros (ϵ_{ij}) and the random effects c_i and g_i . The above nonlinear model analysis will be based on the log-transformed C_{min} values. Data from all subjects together from all dose groups will be used for the analysis.

Time (t_{ss} in days) at which 90% of the subject-specific C_{ss} is achieved (ie, individual steady state attainment) will be calculated from the model, using the equation:

$$t_{ss} = \frac{\log(1 - 0.9)}{-\gamma}$$

Similarly, time (in days) at which 50% of the subject-specific C_{ss} is achieved (ie, average steady state attainment) will also be provided.

In addition, model parameter estimates with standard errors and 90% CIs will be provided. The adequacy of the nonlinear model will be assessed graphically by plotting residual versus dose, residual versus time, and observed (log-scale) and predicted values versus time for individual subjects.

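### The SAP's steady-state PK model has one Css and no dose term for 100, 300 and 600 mg, and its individual time to steady state is the typical subject's value

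*SAP*

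**What the plan says.** Subjects are randomised to "receive 100 mg, 300 mg, or 600 mg PRV-015, or matching placebo, subcutaneously (SC) every" two weeks (SAP 4). For attainment of steady state, SAP 8.8.1.2 fits a nonlinear mixed model to log-transformed trough values. On the log scale it reads:

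log C_ij = log Css + c_i + log(1 − exp(−gamma·exp(g_i)·j)) + e_ij

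Here j is the day, and c_i and g_i are jointly normal with mean 0. Css "is the average steady state trough" concentration and gamma "is the average first-order elimination rate". No parameter depends on dose, and "Data from all subjects together from all dose groups will be used for the analysis". Parameter estimates are to be reported with standard errors and 90% CIs.

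The SAP then defines t_ss as the time to reach 90% of the subject's own Css ("ie, individual steady state attainment) will be calculated from the model, using the equation"). The equation is log(1 − 0.9)/(−gamma), without g_i. A 50% counterpart, described as average attainment, is obtained in the same way.

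On sampling, Protocol 8.1 lists "Trough concentration of PRV-015" at Visit 16 (Day 197) as at the other PK visits. SAP 8.8.1.2 takes Cmin to be the concentration before dosing at the visit. It does not list which visits enter the steady-state model.

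**The concern.** A model with one fixed plateau cannot represent three arms with different plateaus except through the random effect. The population Css then describes a mixture of arms, and the variance of c_i mixes dose with genuine between-subject variability. The other two modelled PK analyses in the same section both carry dose: the power model has log dose as regressor, and the accumulation ANOVA has dose as a fixed effect. The steady-state model is the exception.

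The t_ss equation conflicts with its own description. The model gives each subject a rate gamma·exp(g_i), but the formula drops exp(g_i). A reader of the study report would take the result as information about individuals and would get one number.

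A third, conditional matter is sample eligibility. The model curve can only rise to a plateau. Any sample taken well beyond a dosing interval after the last dose lies on a declining limb that the curve cannot follow.

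**Working it through.** **Figure in the documents.** The protocol places Visit 16 six weeks after the last planned dose. Visit 14 (last dose) is Day 155, Visit 15 is Day 169 and Visit 16 is Day 197 (Protocol 1.3 and 8.1). So 197 − 155 = 42 days = 6 weeks, which agrees, and 169 − 155 = 14 days. Visit 16 is therefore three dosing intervals after the last planned dose and Visit 15 is one. The documents give no value for gamma, Css or any variance, so the PK magnitudes below rest on stated assumptions.

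**One Css for three doses (assuming dose proportionality and equal arms).**
- The pooled log Css is the mean of the arm values, so it corresponds to the geometric mean dose: (100 × 300 × 600)^(1/3) = 262 mg.
- Against the arms: 262/100 = 2.6, 262/300 = 0.87, 262/600 = 0.44.
- Log doses are 4.605, 5.704 and 6.397, with mean 5.569. Deviations are −0.964, 0.135 and 0.828. The variance is (0.928 + 0.018 + 0.686)/3 = 0.544, an SD of 0.74.
- On the concentration scale this is a CV of sqrt(exp(0.544) − 1) = 85%. A within-dose SD of 0.3 becomes sqrt(0.09 + 0.544) = 0.80 after pooling.

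**Does pooling distort t_ss?** Trials were simulated with 50 subjects per dose, 8 trials per setting, dose-proportional PK, the same rate at all doses, SD 0.35 for c_i, 0.30 for g_i and 0.20 for residual error. The plateau at 300 mg was set to 40. Visit 16 was left out.

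| Half-life (assumed) | Model | Css | SD of c_i | t_ss (days) |
|---|---|---|---|---|
| 14 d (true t_ss 46.5) | no dose term | 34.8 | 0.82 | 50.4 |
| 14 d | dose in Css | 39.9 | 0.34 | 50.4 |
| 21 d (true t_ss 69.8) | no dose term | 34.7 | 0.80 | 74.5 |
| 21 d | dose in Css | 39.5 | 0.35 | 74.5 |

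Pooling moves Css (40 × 262/300 = 34.9, as predicted) and more than doubles the SD of c_i. It leaves t_ss where it was. Both fits exceed the true t_ss by the same amount, mainly because j was taken as study day, which runs one day ahead of elapsed time.

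**Individual t_ss.** Setting 1 − exp(−gamma·exp(g_i)·t) = 0.9 gives t_ss,i = ln(10)/(gamma·exp(g_i)). The SAP equation gives ln(10)/gamma = 2.303/gamma, which is the case g_i = 0. The ratio is exp(−g_i):

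| SD of g_i (assumed) | 90% range of t_ss,i relative to the SAP value |
|---|---|
| 0.2 | 0.72 to 1.39 |
| 0.3 | 0.61 to 1.64 |
| 0.5 | 0.44 to 2.28 |

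The 50% version, 0.693/gamma, also uses gamma alone, so both times refer to the typical subject.

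**If Visit 16 entered the model.** From Day 169 to Day 197 there are 28 days without dosing, so the level falls to 2^(−28/half-life) of the Day 169 value: 6% at a half-life of 7 days, 25% at 14 and 50% at 28 (all assumed). In the same simulations, adding Visit 16 took t_ss from 50.4 to 33.2 days (half-life 14) and from 74.5 to 55.1 days (half-life 21).

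**The case against.** **The output that matters is not biased.** The aim is time to steady state, and c_i already lets each subject have their own plateau. This stands while the rate is the same at every dose; a dose-dependent rate would be hidden by the pooled fit. The fault is in Css, its CI and the variance of c_i.

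**The secondary PK endpoint might seem compromised, since it is Cmin.** The documents do not support that inference. SAP 8.8.1.2 summarises Cmin by treatment group and time point, tests proportionality with a power model (by-dose ANOVA as fallback) and estimates accumulation by dose level. None of these uses the steady-state model.

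**It is also tempting to say that c_i must show three clusters.** That depends on the within-dose spread. Under proportionality an equal mixture at the three doses has three peaks for a within-dose SD up to 0.34 and only two from 0.35. Non-normality remains, but the number of peaks is not determined by the plan.

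**The t_ss formula is a labelling matter.** Largely so: it is correct for a subject with g_i = 0. But the text promises a subject-level quantity, and the formula cannot supply one.

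**A reader might infer that the model will be fitted to washout data, because the protocol calls the Visit 16 sample a trough.** No text says so. The same laboratory line appears at Visit 3, before any randomised drug, so it names an assay and not an analysis rule. The SAP's pre-dose definition could be read as excluding Visit 16. Taken literally, though, it would also exclude Visit 15, which the SAP uses for proportionality and accumulation. What stands is that eligibility for this model is unstated.

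**Conclusion.** The point holds as a minor correction to one supporting PK analysis. As written, the SAP would report a Css and 90% CI that describe none of the three arms (about 262 mg if PK is proportional to dose), and a between-subject variance inflated by 0.544 on the log scale. It would also report, as individual, a time to steady state that is identical for everyone.

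The missing dose term and the missing g_i can be read directly from the SAP. The magnitudes depend on assumed proportionality, half-lives and variances. The Visit 16 effect is conditional on that sample entering the model. Efficacy, safety, the by-dose Cmin summaries, proportionality and accumulation are unaffected.

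**What to change.** - Give Css a dose term: a separate Css per dose, or log dose as a covariate on log Css. Report Css and its CI by dose.
- Compute t_ss,i = log(0.1)/(−gamma·exp(g_i)) from each subject's predicted g_i and report the distribution. Keep log(0.1)/(−gamma) as the typical-subject value, and label the 50% version likewise.
- State that the model uses only samples taken about one dosing interval (14 days) after an administered dose, defined by time since last dose. A rule by visit number is not enough: Visit 15 doubles as the early-termination visit, and Protocol 7.1 encourages subjects who stop study drug to keep attending. The time-based rule removes Visit 16 and off-treatment samples together.

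The cost is a few lines of model code and two or three sentences in SAP 8.8.1.2. No data collection changes.
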